7.5. BASELINE DISEASE CHARACTERISTICS

7.5.1. Parameters

- Duration of RA (years) = $\frac{(\text{date of initial diagnosis}) - (\text{screening date}) + 1}{365.25}$, rounded to the nearest integer. If the date of initial diagnosis is incomplete, then the following rules will be applied: Missing day: use the first of the month. Missing month: use January.
- Duration of RA, categorized:
 - <0.5;
 - [0.5,2[;
 - [2,5[;

- [5,10[;
- [10,20[;
- ≥20 years
- Screening and baseline CRP
- Screening and baseline CRP, categorized:
 - <0.7 x ULN;
 - [0.7,1.0] x ULN;
 -]1.0,1.2[x ULN;
 - ≥ 1.2 x ULN
- Change in CRP (baseline – screening)
- Screening and baseline TJC68 and SJC66
- Change in TJC68 and SJC66 = baseline – screening
- Screening and baseline DAS28(CRP) – see further sections for the definition of the DAS28(CRP)
- Change in DAS28(CRP) = baseline – screening
- Screening and baseline patient’s global evaluation of disease activity (0-100 mm VAS)
- Change in patient’s global evaluation of disease activity = baseline – screening
- Baseline investigator’s global evaluation of disease activity (0-100 mm VAS)
- Baseline patient’s pain score (0-100 mm VAS)
- Baseline HAQ-DI
- Baseline SDAI
- Baseline CDAI
- RF status, classified as positive/negative based on the upper limit of the normal range (ULN):
 - o Positive: value > ULN
 - o Negative: < value ≤ ULN
 - o Missing: value is missing for any reason.
- Anti-CCP status, classified as positive/negative based on the upper limit of the normal range (ULN):
 - o Positive: value > ULN
 - o Negative: < value ≤ ULN
 - o Missing: value is missing for any reason.
- Affected joints identification
- Prior RA medication:
 - o Generic names, also classified as: biological (anti-TNF or other biological DMARD), anti-TNF, other biological DMARD, conventional DMARD, NSAID, steroid, analgesic, other RA medication.
 - o MTX duration (study screening date – date of start of MTX + 1 day), expressed in years. If there were multiple dosing periods of MTX, then the “duration” will add up all such episodes.
 - o MTX duration, categorized as:
 - <0.5;
 - [0.5,2[;
 - [2,5[;
 - [5,10[;

- [10,20[;
- ≥20 years
- Steroids (as prednisolone-equivalent): total daily dose at the start of the study
- Steroids (as prednisolone-equivalent): total daily dose at the start of the study, categorized as:
 - <5 ;
 - [5,10[;
 - [10,15[;
 - [15,20[;
 - ≥20 mg/day.

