12.2.8.3. According to the ATP III classifications

The worst-case is the highest post-baseline class for LDL, total cholesterol and triglycerides.
The worst-case is the lowest post-baseline class for HDL.

12.2.9. Tables up to Week 12

No formal inferential statistics (p-values) will be derived. Time points to present: screening, baseline, Weeks 1-2-4-8-12, last on-treatment, worst case.

If the subject did not participate in the second period of the study, then the follow-up visit will be presented in the table of the first period of the study. If the subject participated in the second period of the study, then the follow-up value will be presented in the table of the second period of the study, not of the first period.

Table 14.3.2.1: Laboratory data up to Week 12: Descriptive statistics of the actual values per time point

Descriptive statistics of actual values per lab test category (hematology, biochemistry, endocrine, urinalysis), lab test and unit, treatment group and time point.

Population: safety.

Population: safety, selecting subjects with a baseline value within normal range (for endocrine tests only).

Table to be created for the Week 12 interim analysis as well.

Table 14.3.2.2: Laboratory data up to Week 12: Descriptive statistics of the changes from baseline per time point

Descriptive statistics of changes from baseline per lab test category (hematology, biochemistry, endocrine, urinalysis), lab test and unit, treatment group and time point. The actual value at baseline will also be presented in this table.

Population: safety.

Population: safety, selecting subjects with a baseline value within normal range (for endocrine tests only).

Table to be created for the Week 12 interim analysis as well.

Table 14.3.2.3: Laboratory data up to Week 12: Descriptive statistics of the percent changes from baseline per time point

Descriptive statistics of percent changes from baseline per lab test category (hematology, biochemistry, endocrine, urinalysis), lab test and unit, treatment group and time point. The actual value at baseline will also be presented in this table.

Population: safety.

Population: safety, selecting subjects with a baseline value within normal range (for endocrine tests only).

Table to be created for the Week 12 interim analysis as well.

Table 14.3.2.4: Laboratory data up to Week 12: Shift table of the lab abnormalities per time point

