Shift table per lab test category (hematology, biochemistry, endocrine, urinalysis), lab test, treatment group and time point. The table will present the shift in abnormality (L/N/...) at worst-case and last on-treatment (other time points: not needed) versus the baseline abnormality (L/N/H). Tests without normal ranges will not be presented in this table.

Population: safety.

Table 14.3.2.5: Laboratory data up to Week 12: Treatment-emergent lab abnormalities per time point

Frequency table of the treatment-emergent lab abnormalities per lab test category (hematology, biochemistry, endocrine, urinalysis), lab test, treatment group and time point (including the worst-case). A post-baseline abnormality is considered treatment-emergent if it differs from the baseline result. Tests without normal ranges will not be presented in this table.

Population: safety.

Table to be created for the Week 12 interim analysis as well.

Table 14.3.2.6: Laboratory data up to Week 12: Frequency table of the CTCAE toxicity grades per time point

Frequency table (with cumulative percentages) per lab test category (hematology, biochemistry, endocrine, urinalysis), lab test, treatment group and time point.

Table for selected tests only.

Population: safety.

Table to be created for the Week 12 interim analysis as well.

Table 14.3.2.7: Laboratory data up to Week 12: Shift table of the CTCAE toxicity grades per time point

Shift table per lab test category (hematology, biochemistry, endocrine, urinalysis), lab test, treatment group and time point. The table will present the shift in CTCAE tox grade (0/1/2/3/4) at worst-case and last on-treatment (other time points: not needed) versus the baseline grade (0/1/2/3/4).

Table for selected tests only.

Population: safety.

Table 14.3.2.8: Laboratory data up to Week 12: Treatment-emergent CTCAE toxicity grades per time point

Frequency table of the treatment-emergent lab CTCAE tox grades per lab test category (hematology, biochemistry), lab test, treatment group and time point (including worst-case). A

post-baseline grade is considered treatment-emergent if it is higher than the baseline tox grade.

Table for selected tests only.

Population: safety.

Table to be created for the Week 12 interim analysis as well.

Table 14.3.2.9: Laboratory data up to Week 12: Frequency table of the ATP III classes per time point

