Frequency table (with cumulative percentages) per lab test category (hematology, biochemistry, endocrine, urinalysis), lab test, treatment group and time point.

Table for selected tests only.

Population: safety.

Table to be created for the Week 12 interim analysis as well.

Table 14.3.2.10: Laboratory data up to Week 12: Shift table of the ATP III classes per time point

Shift table per lab test category (hematology, biochemistry, endocrine, urinalysis), lab test, treatment group and time point. The table will present the shift in ATP III class at worst-case and last on-treatment (other time points: not needed) versus the baseline class.

Table for selected tests only.

Population: safety.

Table 14.3.2.11: Laboratory data up to Week 12: Treatment-emergent ATP III classes per time point

Frequency table of the treatment-emergent lab ATP III classes per lab test category (hematology, biochemistry), lab test, treatment group and time point (including worst-case). A post-baseline class is considered treatment-emergent if it differs from the baseline result and is of higher category.

Table for selected tests only.

Population: safety.

Table to be created for the Week 12 interim analysis as well.

Table 14.3.2.12: Laboratory data up to Week 12: Frequency table of percent changes from baseline per time point in inhibin B and testosterone

Frequency table of the percent changes from baseline per lab test category (endocrine), lab test, treatment group and time point. The percent changes from baseline will be categorized

as: <-50%, [-50%,+50%], >+50%. A worst-case will also be shown selected as the lowest post-baseline value.

Table only for inhibin B, free testosterone, total testosterone.

Population: safety – males.

Population: safety, selecting male subjects with a baseline value within normal range.

Table to be created for the Week 12 interim analysis as well.

Table 14.3.2.13: Laboratory data up to Week 12: Shift table of the categorical lab data per time point

Shift table per lab test category (hematology, biochemistry, endocrine, urinalysis), lab test, treatment group and time point. Selecting only the tests with categorical data. The table will present the shift in value at each post-baseline time point versus the baseline value.

Population: safety.

12.2.10. Figures up to Week 12

Figure 14.3.2.1: Laboratory data up to Week 12: Mean plots of the actual values over time

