12.2.11. Tables over the whole 24 weeks period

The same tables will be made as for the first period of the study, but with the 5 adapted treatment groups. Time points to present: screening, baseline, Week 1-2-4-8-12, last on-treatment during period 1, worst case during period 1, Weeks 16-20-24, last on-treatment during period 2, follow-up (all follow-up visits in the study), worst case during period 2, last on-treatment during the whole study, worst case during the whole study. Population: Safety.

Table 14.3.2.14: Laboratory data over the whole study: Descriptive statistics of the actual values per time point

Table 14.3.2.15: Laboratory data over the whole study: Descriptive statistics of the changes from baseline per time point

Table 14.3.2.16: Laboratory data over the whole study: Descriptive statistics of the percent changes from baseline per time point

Table 14.3.2.17: Laboratory data over the whole study: Shift table of the lab abnormalities per time point

Table 14.3.2.18: Laboratory data over the whole study: Treatment-emergent lab abnormalities per time point

Table 14.3.2.19: Laboratory data over the whole study: Frequency table of the CTCAE toxicity grades per time point

Table 14.3.2.20: Laboratory data over the whole study: Shift table of the CTCAE toxicity grades per time point

Table 14.3.2.21: Laboratory data over the whole study: Treatment-emergent CTCAE toxicity grades per time point

Table 14.3.2.22: Laboratory data over the whole study: Frequency table of the ATP III classes per time point

Table 14.3.2.23: Laboratory data over the whole study: Shift table of the ATP III classes per time point

Table 14.3.2.24: Laboratory data over the whole study: Treatment-emergent ATP III classes per time point

Table 14.3.2.25: Laboratory data over the whole study: Frequency table of percent changes from baseline per time point in inhibin B and testosterone

Table 14.3.2.26: Laboratory data over the whole study: Shift table of the categorical lab data per time point

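### Two SAP derivations run in the wrong direction: the ATP III treatment-emergent rule counts HDL class rises and no falls, and RA duration comes out as zero or negative

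*SAP*

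**What the plan says.** **HDL.** SAP 12.2.5.4 lists three HDL classes in ascending order: below 40, 40 to below 60, and 60 mg/dL or more. SAP 12.2.8.3 sets the adverse direction: "The worst-case is the lowest post-baseline class for HDL". For LDL, total cholesterol and triglycerides the highest class is the worst. In SAP 12.2.9, Table 14.3.2.11 applies one rule to every test it shows: "A post-baseline class is considered treatment-emergent if it differs from the baseline result and is of higher category". Its scope is given only as "Table for selected tests only", and the tests are not named. The table is also an interim output. SAP 12.2.11 carries the rule into Table 14.3.2.24: "The same tables will be made as for the first period of the study, but with the 5 adapted treatment groups".

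**RA duration.** SAP 7.5.1 defines "Duration of RA (years") as the date of initial diagnosis minus the screening date plus 1, divided by 365.25, and then "rounded to the nearest integer. If the date of initial diagnosis is incomplete" gives rules for partial dates. A few lines further down, methotrexate duration has the dates in the opposite order: "MTX duration (study screening date" comes first and the start date is subtracted. Protocol 8.3.2 (criterion 2) requires the RA diagnosis to be at least 6 months old at Screening.

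**The concern.** The HDL rule appears to be modelled on the CTCAE rule for Table 14.3.2.8, where a "post-baseline grade is considered treatment-emergent if it is higher than the baseline tox grade". That works for toxicity grades because a higher grade is always worse. It does not work for HDL, where a higher class is better. The HDL rows would then present improvements under a treatment-emergent heading and leave out the deteriorations. Protocol 6.1 lists increased HDL among the effects seen with tofacitinib, so rises are plausible here and the rows could hold believable counts that nobody questions.

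The RA-duration formula gives a number with the wrong sign. It feeds the baseline disease tables (14.1.3.7 to 14.1.3.9), the duration split in Tables 14.2.1.1.7 and 14.2.1.4.6, and the exploratory models in Tables 14.2.1.1.8 and 14.2.1.4.7. Several of these are interim outputs.

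**Working it through.** The plan gives no numerical result for either rule, so each was applied as written and then with the direction reversed.

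**HDL**

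1. Three classes give 3 × 3 = 9 baseline-by-post-baseline pairs: 3 rises, 3 falls, 3 unchanged.
2. Under the rule (post-baseline class above baseline class), 3 of 3 rises are counted and 0 of 3 falls.
3. The worst-case column takes the lowest class over Weeks 1, 2, 4, 8 and 12 and then asks whether it lies above baseline. Five visits give 3^5 = 243 possible class patterns (counts of patterns, not probabilities):

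| Baseline class (mg/dL) | Patterns flagged as written | Patterns containing a fall |
|---|---|---|
| <40 | 2^5 = 32, all improvements | 0 |
| 40 to <60 | 1 (every visit ≥60) | 243 − 2^5 = 211 |
| ≥60 | 0 | 243 − 1 = 242 |

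4. With the direction reversed for HDL, the 3 falls are counted and the 3 rises are not. LDL, total cholesterol and triglycerides already run the right way.

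**RA duration**

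Let d be the number of days from diagnosis to Screening. As written, the value is (1 − d)/365.25; with the dates reversed it is (d + 1)/365.25. Both are rounded to the nearest integer. Six calendar months is 181 to 184 days.

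| d (days) | As written | Rounded | Dates reversed | Rounded |
|---|---|---|---|---|
| 181 | −0.493 | 0 | 0.498 | 0 |
| 183 | −0.498 | 0 | 0.504 | 1 |
| 184 | −0.501 | −1 | 0.507 | 1 |
| 2557 (7 years) | −6.998 | −7 | 7.003 | 7 |
| 7305 (20 years) | −19.997 | −20 | 20.003 | 20 |

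- For every d from 181 days upward, the largest rounded value as written is 0. All eligible subjects with a known diagnosis date therefore fall below 0.5 years in the baseline tables and below 1 year in Tables 14.2.1.1.7 and 14.2.1.4.6.
- The partial-date rules (first of the month, January) move the diagnosis earlier, so they cannot make the value positive.
- The Cochran-Mantel-Haenszel general-association test in SAP 7.5.2, with 4 groups and 6 categories, has up to (4 − 1)(6 − 1) = 15 degrees of freedom. With one filled category it has (4 − 1)(1 − 1) = 0 and cannot be computed.
- The rounded value as written is almost always the exact negative of the corrected one and never differs from that negative by more than 1 year. If duration enters the stepwise model of Table 14.2.1.1.8, its per-year odds ratio becomes about its reciprocal. An illustrative 0.97 would print as 1/0.97 ≈ 1.03.
- Table 14.2.1.4.7 reports type-III p-values and LS-means, which are essentially unchanged. Only the raw SAS appendix would show the reversed sign.

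**The case against.** **On HDL.** The table covers selected tests only and its layout is in a separate mock document, so HDL might not be included. That condition stands, but HDL has its own ATP III classes and its own worst-case rule, which makes inclusion the natural reading.

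HDL falls are also visible elsewhere. The ATP III frequency table and the descriptive tables show them indirectly. Table 14.3.2.5 counts any abnormality that differs from baseline, so it would show new low HDL if the laboratory supplies a normal range. The TC/HDL and LDL/HDL ratios in SAP 12.2.2, which have stated ranges, rise when HDL falls, other things equal. The shift table (14.3.2.10) shows falls directly, but only at worst case and last on-treatment, and it is not marked for the interim. All of this limits the harm; it does not correct the rule. Reading higher as worse is not supported, because SAP 12.2.8.3 uses highest and lowest in value order.

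**On RA duration.** The intent is obvious from the label, the positive categories and the methotrexate formula. Negative durations would probably be noticed on first output. The list of changes after the interim lock (SAP 6.3.2) amends the baseline disease table without mentioning a duration problem, which makes a slip in the text alone more likely than a slip in the code. That is a fair inference but not proof, and if the programs departed from the SAP, no record of it appears there.

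**Conclusion.** Both derivations are wrong as written, and the severity is minor. If HDL is among the tests shown and the rule is programmed literally, its rows in Tables 14.3.2.11 and 14.3.2.24 report 3 of 3 rises and 0 of 3 falls. If the duration formula is programmed literally, every eligible subject with a known diagnosis date has a value of 0 or below and sits in a single category. The category test then has no degrees of freedom, the subgroup split disappears, and any odds ratio for duration is inverted. The HDL error is the easier one to miss, because its counts would look plausible. Neither error touches the primary ACR20 analysis at Week 12, the sample size or the type I error.

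**What to change.** 1. In the text for Table 14.3.2.11 (and so 14.3.2.24), define a treatment-emergent ATP III class as one worse than baseline: higher for LDL, total cholesterol and triglycerides, lower for HDL. Name the tests the table covers.
2. In SAP 7.5.1, write RA duration as (screening date − date of initial diagnosis + 1)/365.25, in line with the methotrexate formula.
3. Check which direction the interim programs used in Table 14.3.2.11, the baseline disease tables and Table 14.2.1.1.7, and record the result in the SAP's list of changes.

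While SAP 7.5.1 is open, it should also say that the duration categories use the unrounded value: 548 days is 549/365.25 = 1.503 years, which rounds to 2 and would move from the 0.5 to <2 category into 2 to <5.

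The cost is two lines of SAP text, matching code and a check of existing tables. No data change.

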12.2.11. Tables over the whole 24 weeks period

The same tables will be made as for the first period of the study, but with the 5 adapted treatment groups. Time points to present: screening, baseline, Week 1-2-4-8-12, last on-treatment during period 1, worst case during period 1, Weeks 16-20-24, last on-treatment during period 2, follow-up (all follow-up visits in the study), worst case during period 2, last on-treatment during the whole study, worst case during the whole study. Population: Safety.

Table 14.3.2.14: Laboratory data over the whole study: Descriptive statistics of the actual values per time point

Table 14.3.2.15: Laboratory data over the whole study: Descriptive statistics of the changes from baseline per time point

Table 14.3.2.16: Laboratory data over the whole study: Descriptive statistics of the percent changes from baseline per time point

Table 14.3.2.17: Laboratory data over the whole study: Shift table of the lab abnormalities per time point

Table 14.3.2.18: Laboratory data over the whole study: Treatment-emergent lab abnormalities per time point

Table 14.3.2.19: Laboratory data over the whole study: Frequency table of the CTCAE toxicity grades per time point

Table 14.3.2.20: Laboratory data over the whole study: Shift table of the CTCAE toxicity grades per time point

Table 14.3.2.21: Laboratory data over the whole study: Treatment-emergent CTCAE toxicity grades per time point

Table 14.3.2.22: Laboratory data over the whole study: Frequency table of the ATP III classes per time point

Table 14.3.2.23: Laboratory data over the whole study: Shift table of the ATP III classes per time point

Table 14.3.2.24: Laboratory data over the whole study: Treatment-emergent ATP III classes per time point

Table 14.3.2.25: Laboratory data over the whole study: Frequency table of percent changes from baseline per time point in inhibin B and testosterone

Table 14.3.2.26: Laboratory data over the whole study: Shift table of the categorical lab data per time point

12.2.12. Figures over the whole 24 weeks period

The follow-up visit will not be shown on the mean plots because it is expected that it will happen only for a limited number of subjects, as a large number will roll over into study 205 without a follow-up visit.

The same plots again, but with the 5 adapted treatment groups. Plots will show data from screening up to the end of the study.

Figure 14.3.2.4: Laboratory data over the whole study: Subject profile plots over time – subjects with a treatment-emergent abnormality

Figure 14.3.2.5: Laboratory data over the whole study: Mean plots of the actual values over time

Figure 14.3.2.6: Laboratory data over the whole study: Mean plots of the changes from baseline over time

Figure 14.3.2.7: Laboratory data over the whole study: Mean plots of the percent changes from baseline over time

12.2.13. Listings

All listings will contain next to the actual data (raw and changes) the following parameters:

- a fasted Y/N flag
- an abnormality L/H flag
- CTCAE toxicity grade, ATP III classification
- the test's normal range
- a clinical relevance flag

Listing 16.2.11.1: Laboratory data: Full listing

Listing per treatment group, per subject and per time point of all recorded data.

Population: safety.

Listing 16.2.11.2: Laboratory data: Abnormalities listing

Listing per treatment group, per subject and per time point of all data scored as out-of-normal-range, plus also the baseline reference time point.

Population: safety.

Listing 16.2.11.3: Laboratory data: Clinically significant abnormalities

Listing per treatment group, per subject and per time point of the eCRF's verbatim text field on clinically significant abnormalities.

Population: safety.

Listing 16.2.11.4: Laboratory data: Urinalysis results

Listing per treatment group, per subject and per time point of the urinalysis results.

Population: safety.

Listing 16.2.11.5: Laboratory data: Positive pregnancy tests

Listing per treatment group, per subject and per time point of all pregnancy test results (urine and serum) for female subjects who had a positive test at some point.

Population: safety.

12.3. ECG

12.3.1. Available Data

Available parameters: HR, QRS, QT, and an interpretation. The RR interval, when available, will only be listed.

